13.3.3 Definitive stage

The primary analysis of the study is the comparison of clinical progression-free survival between the two study arms.

Assuming that proportional hazards holds, a Cox proportional hazards model will be generated to model the progression-free survival times on the two study arms. Variables that will be entered into the model will include: patient descriptive variables (age, gender, etc.); centre of recruitment, the initial diagnosis of tumour grade at randomisation (stratification group) and the initial cystoscopic assessment of probable NMIBC vs. the remainder.

If the proportional hazards assumption does not hold; the comparison between arms will be performed at a set follow up point for all patients. To ensure that both progressions and recurrences are captured, the analysis will be performed at the final patient follow up point.

Secondary analyses

Descriptive statistics will be produced and subgroup analyses comparing MIBC and NMIBC outcomes between each arm will also be conducted.

Secondary analyses will include a Cox regression model comparing the TTDT of all patients (i.e. comparing TTDT for patients who pass through boxes A-D in the study flow diagram) and for the probable NMIBC patients (boxes A and C). Recurrence rates; overall and disease specific survival will also be calculated for each arm.

13.4 Planned subgroup analyses

Subgroup analyses will be conducted in the definitive stage according to:

- Initial diagnoses: possible MIBC or probable NMIBC
- Final diagnosis type: MIBC or NMIBC

- Multifocal vs. single invasive cancer
- Men vs. women
- Age stratified

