Appendix	x 1 - World Medical Association Declaration of Helsinki	39	
	Appendix 2 - Definition of Adverse Events 42		
Appendix	x 3 - Common Toxicity Criteria Gradings	42	

BACKGROUND AND RATIONALE 1.

Background 1.1

Bladder cancer is the fifth most common cancer in western society, with a rising global incidence and 430,000 new cases in 2012^{1,2}. In the UK there are approximately 10,000 new cases and 5,000 deaths attributed to bladder cancer annually³. In western populations, over 90% of bladder cancers are urothelial cell carcinoma (UCC). Standard management follows a pattern established during the 1950s with the development of the rigid cystoscope. Prognosis has not improved in the last 30 years³⁻⁵.

Standard management involves a pathway of diagnostic flexible cystoscopy followed by a transurethral resection of the bladder tumour (TURBT) with a rigid cystoscope. TURBT has the multiple purposes of diagnosis, staging and treatment of non-muscle invasive bladder cancer (NMIBC), i.e. removal of the tumour. Further treatment such as radical cystectomy or chemoradiotherapy is then necessary for muscle invasive bladder cancer (MIBC).

For MIBC, this initial TURBT often understages invasion (up to 30% of MIBCs are initially staged as high grade NMIBC at first TURBT)⁶, and may contribute to extra-vesical tumour dissemination through bladder perforation or venous emboli generated through the high-pressure resection process⁷. Crosssectional pelvic imaging after TURBT impedes the accuracy of staging due to surgical artefacts (such as perivesical inflammation and reactive lymph nodes)⁸⁻¹¹.

Typically, the need for a TURBT, histopathological review and MDT decision-making adds at least 6-12 weeks to the pathway, prolonging the delay to commencing (the most appropriate) definitive radical treatment for patients with MIBC^{6, 12-14}.

An ideal pathway would separate NMIBC patients from MIBC patients at the time of diagnosis. Faster and more accurate application of established technologies would streamline therapy, potentially improve outcomes and save clinical costs.

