For the 75-80% of bladder cancer patients who present with NMIBC, tumour recurrence and progression following TURBT are significant issues, compelling current guidelines to recommend intense long-term surveillance by cystoscopy and urine cytology¹⁵. With the UK prevalence of bladder cancer estimated at 46,500, at any one time there will be 35-37,000 patients with NMIBC requiring such surveillance, performed as often as every 3 to 6 months at an estimated cost of at least £533 per flexible cystoscopy/cytology "episode" (as costed in 2010¹⁶). Around 30% of NMIBC cases will progress to MIBC and require additional therapy.

Around 20-25% of new bladder cancer patients present with *de novo* MIBC^{17,18}. Survival with MIBC remains poor (27-50% five-year survival) and has not improved in 30 years³. The present pathway is largely geared to NMIBC and actively delays effective MIBC treatment, which is often carried out in a different hospital to initial diagnosis and TURBT, increasing handovers and therefore delays. In Birmingham, for example, many National Health Service (NHS) Trusts run haematuria clinics, a smaller number (but at least six) offer systemic chemotherapy, but only two carry out major pelvic surgery and only one radiotherapy. Early clarity on staging and diagnosis would facilitate more coordinated planning and treatment delivery. Similar considerations exist in all major healthcare systems worldwide.

This fragmented care with complicated staging and follow-up leads to the cumulative cost of treating bladder cancer exceeding all other forms of human cancer.

The standard shared patient pathway thus delays therapy for MIBC patients. There is a growing body of opinion that such pathways should separate earlier in order to more appropriately and expeditiously treat MIBC patients⁴, and this is what we propose to evaluate here.

1.2 **Staging and Treatment**

The pros and cons of staging and treatment techniques for bladder cancer are summarised below, including the aim of TURBT in the settings of NMIBC and MIBC.

Table 1.			
Aim of TURBT	NMIBC	MIBC	
Diagnosis	\checkmark	\checkmark	
Staging	\checkmark	Sometimes – understaging in up to 30%	

Table 4 Aim of TUDDT in NMIDC and MIDC

Table 1.	Aim of TURBT in NMIBC and MIBC	
Aim of TURBT	NMIBC	MIBC
Treatment	\checkmark	No – may be harmful
Palliation of symptoms	Sometimes in cases of heavy bleeding	Sometimes in cases of heavy bleeding.

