1.4 Rationale

The prognosis for MIBC remains poor and has not changed for three decades³⁻⁵. Modern MRI approaches now have the ability to accurately stage bladder tumours^{11,19-23} and experimental urinary biomarkers show great promise in identifying MIBC from a urine test with high sensitivity and specificity²⁴⁻²⁶. The platforms therefore exist to improve patient pathways, potentially leading to improved outcomes.

In order to change the current pathway, we need to show that alternatives to TURBT exist for staging, and that faster treatment will improve outcomes.

- 1. Do we need TURBT for histology?
 - a. Flexible cystoscopy can give accurate tumour histological diagnosis and grading but does not assess muscle-invasion.
- 2. Can we replace TURBT for detailed assessment of the bladder tumour?

- a. TURBT is frequently inaccurate and operator dependent up to 30% of tumours assessed as high grade NMIBC at TURBT are subsequently diagnosed as invasive (MIBC) on repeat TURBT or at cystectomy^{6, 27}.
- Buidelines recommend repeat TURBT for patients staged G3pT1 because of the high incidence of under staging – further delaying definitive treatment in some patients with MIBC^{6,27}
- c. Sensitivity and specificity of mpMRI for separating NMIBC from MIBC are 94% and 100%, respectively^{11, 19-23}
- d. Substituting MRI for TURBT should not compromise staging and may improve it.
- 3. Is TURBT an essential component of treatment?
 - a. There are no randomised data on this topic this is one of the aims of this study.
 - b. Evidence exists that TURBT may increase local tumour dissemination²⁸ and lead to increases in circulating tumour cells⁷.
 - c. In most other oncology settings, imaging and biopsy are sufficient for definitive treatment; in some cases imaging alone is sufficient (e.g. kidney cancer and upper tract urothelial cancer). Few tumour sites use an intermediate piecemeal debulking ahead of definitive therapy²⁹.
- 4. Does delaying the correct definitive treatment affect prognosis?
 - Typical duration from first clinic visit to correct definitive treatment within the NHS for MIBC is around 100 days^{17, 30, 31}
 - b. There is evidence that delay can affect prognosis for MIBC¹²⁻¹⁴
 - c. Hence reducing delay should improve prognosis.

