6.1.2 Randomisation procedure

If the patient is subsequently given a diagnosis of suspected bladder cancer and would still like to take part in the study, the patient will sign a second Informed Consent Form and will be randomised into the study.

Randomisation will be done online via the via the online electronic remote data capture system (eRDC) by logging on to: https://www.cancertrials.bham.ac.uk

An Eligibility Checklist must be completed and faxed to the Study Office before the online Randomisation Form is completed.

At the end of the randomisation procedure a report should be printed as a confirmation and filed in the Investigator Site File along with the original signed Informed Consent Form.

Emergency randomisation

If there are any problems with online randomisation, a paper eligibility checklist and randomisation form should be completed. These details should then be phoned through to the Study Office using the numbers below:

2 [name]; 9am-5pm Monday to Friday

Randomisation will be performed using minimisation on a 1:1 basis with the following stratification variables:

- Patient sex: male or female
- Age: <75 years old or ≥75 years old
- Clinician assessment: probable NMIBC or possible MIBC

The randomisation is not blinded, and therefore both participant and the health care team will know which pathway has been allocated to the participant.

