7.1.1 TURBT

Transurethral resection of the bladder tumour should be conducted as recommended by the European Association of Urology (EAU) and British Association of Urological Surgeons (BAUS). In particular, resection of the exophytic component should be performed using a rigid resectoscope. Sampling of the underlying detrusor muscle is necessary, as is recording of the clinical stage following resection (complete, incomplete, semi-fixed, fixed mass etc.). Bladder neck or urethral sampling should be performed in patients suitable for neobladder reconstruction. Sampling of areas suspicious of carcinoma in situ (red areas or fluorescent with blue light) should be undertaken. A separate biopsy of the bladder tumour base should be taken. All samples should be sent for histopathological reporting and reviewed at a suitable clinical meeting.

7.2 Image-directed Pathway 2

Instead of TURBT, patients identified as possible MIBC patients will undergo mpMRI.

Criteria for diagnosing patients as possible MIBC are as follows:

- 1. Appearance on flexible cystoscopy
 - This includes the presence of a solid tumour in the bladder or a tumour seen infiltrating into the bladder wall or a solid tumour or mixed solid/papillary morphology.
 - This may also include the presence of a semi-fixed mass within the bladder found by examination before or after the flexible cystoscopy.
- 2. Cytological: The presence of high grade urothelial cells in either the urine cytology or in the flexible cystoscopy biopsy
- 3. If suitable, imaging obtained (e.g. CT Urography). This may also be used to identify possible MIBC.

The endoscopist carrying out the flexible cystoscopy will be asked to assess the likelihood that a bladder tumour is muscle invasive. If yes, and if either urine cytology or a biopsy taken at cystoscopy confirms the presence of high grade urothelial cancer cells then randomisation between pathways 1 and 2 is permitted.

Treatment proceeds via the standard pathway (without randomisation) for patients with either low grade histology or inconclusive visual appearances on cystoscopy.

7.2.1 mpMRI

Imaging will be carried out as per the Imaging Manual. The scans should be initially read at the local centre but secondary central reading by a certified radiologist will be performed for quality assurance and further research purposes.

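### The planned between-arm subgroup comparison by final diagnosis (MIBC/NMIBC) rests on a post-randomisation stage label that the two pathways reach by different routes, so it is not a randomised comparison and can be biased by stage migration

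*Protocol*

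**What the plan says.** Section 13.4 of the protocol lists the definitive-stage subgroups. Two concern disease stage: "Initial diagnoses: possible MIBC or probable NMIBC" and "Final diagnosis type: MIBC or NMIBC". Section 13.3.3, under secondary analyses, makes clear that these are contrasts between the arms: "subgroup analyses comparing MIBC and NMIBC outcomes between each arm will also be conducted".

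The two stage factors differ in timing. The initial assessment exists before allocation and is a minimisation factor in Section 6.1.2: "Clinician assessment: probable NMIBC or possible MIBC". The final diagnosis comes later, and the protocol states no definition, time point or reference standard for it.

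The staging route depends on the arm. Section 7.1 sends pathway 1 patients with a bladder lesion to TURBT. Section 7.2 says of pathway 2: "Instead of TURBT, patients identified as possible MIBC patients will undergo mpMRI". The protocol also gives the two tools different accuracy. For TURBT, Section 1.1 says "up to 30% of MIBCs are initially staged as high grade NMIBC at first TURBT". For MRI, Section 1.4 says "Sensitivity and specificity of mpMRI for separating NMIBC from MIBC are 94% and 100%, respectively".

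**The concern.** A subgroup supports a randomised comparison when membership cannot be affected by the allocation. Here it can be. The pathways differ in how stage is established, and more accurate staging is one of the aims in Section 2.1. If pathway 2 works as intended, some patients with true MIBC will be labelled MIBC in pathway 2 who would have been labelled NMIBC in pathway 1. The labelled MIBC group then holds a different mix of patients in each arm, and so does the labelled NMIBC group. A hazard ratio inside either label combines any pathway effect with this reclassification.

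The stakes lie in interpretation. The hypothesis in Section 2.1 concerns outcomes in MIBC, so readers will look for a hazard ratio in confirmed MIBC. It would sit beside baseline subgroups (initial diagnosis, sex, age) with nothing to mark it as a different kind of contrast.

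**Working it through.** **Basis.** The plan's own figure reproduces. For HR 0.75 at 80% power with two-sided alpha 0.05 (assumed; the protocol states none), the Schoenfeld formula gives 4 × (1.960 + 0.842)² / (ln 0.75)² = 379.4, i.e. 380 events. At a 40% event rate this is 380 / 0.40 = 950 patients, or 475 per arm.

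**Inputs from the protocol.** Share of MIBC: "Around 20-25% of new bladder cancer patients present with" de novo MIBC (Section 1.1). Label sensitivity: 70% in pathway 1 (100% − 30%) and 94% in pathway 2. Specificity: 100% for mpMRI, and taken as 100% for TURBT. Overall 2-year event rate: 40% (Section 13.2.3).

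**Assumptions.** No pathway effect, exponential times, 2 years of follow-up. The 2-year CPFS risk in true MIBC is varied from 30% to 80%. The NMIBC risk is set so that the overall rate is 40% when missed and detected MIBC share the same risk; giving missed cases another risk moves the overall rate to between 38% and 41%.

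**Step 1, label shift per 475-patient arm.**
- 20% MIBC: 95 true cases. Labelled MIBC: 95 × 0.70 = 67 in pathway 1 and 95 × 0.94 = 89 in pathway 2.
- 25% MIBC: 119 true cases (118.75). Labelled MIBC: 83 in pathway 1 and 112 in pathway 2.

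**Step 2, labelled NMIBC.** Worked case: 25% MIBC, risk 60% in MIBC, so NMIBC risk = (0.40 − 0.25 × 0.60) / 0.75 = 33.3%.
- True MIBC within the label: 0.075 / 0.825 = 9.1% in pathway 1; 0.015 / 0.765 = 2.0% in pathway 2.
- Group risks: 0.333 + 0.267 × 0.091 = 0.358, and 0.333 + 0.267 × 0.020 = 0.339.
- Null HR ≈ ln(1 − 0.339) / ln(1 − 0.358) = 0.93.

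**Step 3, labelled MIBC.** Pathway 1 holds only the detected 70%. Pathway 2 adds 24 points of cases that first TURBT would have missed. Same case, with missed cases midway between MIBC and NMIBC risk (46.7%):
- Pathway 2 risk: (0.70 × 0.60 + 0.24 × 0.467) / 0.94 = 0.566, against 0.60 in pathway 1.
- Null HR ≈ ln(0.434) / ln(0.40) = 0.91.

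**Step 4, range.** These are expected Cox hazard ratios, pathway 2 versus pathway 1, with no true effect. The log-ratio shortcut used above agrees to within about 0.01.

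| MIBC share | MIBC risk | Missed MIBC | HR, labelled NMIBC | HR, labelled MIBC |
|---|---|---|---|---|
| 25% | 30% | same as detected | 1.03 | 1.00 |
| 20–25% | 40% | same as detected | 1.00 | 1.00 |
| 20% | 60% | same as detected | 0.95 | 1.00 |
| 25% | 60% | same as detected | 0.93 | 1.00 |
| 25% | 60% | midway | 0.97 | 0.91 |
| 25% | 80% | same as detected | 0.85 | 1.00 |
| 25% | 80% | midway | 0.92 | 0.83 |
| 22.5% | 60% | worse (75%) | 0.91 | 1.11 |

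The two extremes in favour of pathway 2 do not occur together: 0.85 in NMIBC goes with 1.00 in MIBC, and 0.83 in MIBC goes with 0.92 in NMIBC.

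**Step 5, checks.** The all-patient null HR is 1.00 in every scenario. With strata defined by the assessment made before allocation, patients cannot change stratum and the null HR is 1.00 in each.

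**The case against.** **The label is not defined as the first TURBT or MRI result.** This stands in part. The 30% in Section 1.1 is a first-TURBT figure. Section 1.4 notes that such tumours are later found invasive at repeat TURBT or cystectomy, and that guidelines recommend repeat TURBT for G3pT1. Section 2.2 also lists the accuracy of MRI/TURBT against histologically confirmed diagnosis, which suggests a separate reference. A final label could therefore recover some of the understaging, and one reference standard with equal sensitivity in both arms would bring the null HR back to 1.00. But the protocol names no such standard for this subgroup. A definition may be left to the analysis plan; the commitment to compare arms within the label is already in the protocol.

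**The 94% does not apply to every MIBC in pathway 2.** This stands. Only possible MIBC patients have MRI instead of TURBT, so a true MIBC judged probable NMIBC lies outside that route. With the wording "up to" 30%, this makes the shifts in Step 1 upper bounds. Section 1.4 also states the 30% with a different denominator, as a share of tumours called high grade NMIBC.

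**The direction is open.** This stands. A reader might infer that stage migration by itself favours pathway 2 in both groups. In labelled NMIBC that needs a higher CPFS event rate in MIBC. Section 1.1 supports poor survival in MIBC, but CPFS in Section 13.1 also counts non-muscle-invasive recurrence, and no rate by stage is given. In labelled MIBC it needs missed cases to do better than detected ones. Equal risks give 1.00, and the opposite ordering reverses the sign.

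**The bias is small against random error.** This is partly true. In the 25%/60% midway case, labelled MIBC yields about 83 × 0.60 = 50 and 112 × 0.566 = 63 events, so SE(log HR) = √(1/50 + 1/63) ≈ 0.19, while ln 0.91 ≈ −0.09. That is about half a standard error. At 80% risk the bias is about one standard error (67 and 82 events, SE ≈ 0.16; ln 0.83 ≈ −0.19).

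**It is only a secondary subgroup.** True, and it limits the weight of the point.

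**Conclusion.** The concern holds in limited form. Sections 13.3.3 and 13.4 commit to a between-arm comparison within a label that is set after randomisation, by routes that differ by arm and that the protocol says differ in accuracy, without a common reference standard. That comparison is not protected by randomisation, whichever way the bias runs.

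With no true effect, the null HR runs from about 0.85 to 1.03 in labelled NMIBC and from about 0.83 to 1.11 in labelled MIBC, against a design target of 0.75. Pathway 2 is the likely beneficiary, but the document does not establish this. The range rests on assumed stage-specific risks, exponential times and the full 30% versus 6% gap in missed MIBC, which is an upper bound.

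The primary CPFS comparison of whole arms is unaffected, and so is the subgroup by initial diagnosis. A reader might take the point as a threat to the trial's main conclusion; it is not. It should be corrected before the definitive analysis, as a matter of a secondary analysis.

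**What to change.** In Sections 13.3.3 and 13.4, base between-arm comparisons by disease stage on the initial diagnosis at randomisation (possible MIBC / probable NMIBC). It is already collected, already listed and already a minimisation factor. Keep outcomes by final diagnosis as a descriptive report, with a statement that they are not a randomised comparison. Say how final diagnosis is established, by which reference standard and at what time, so that the descriptive tables can be read.

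The cost is wording only: no new data, no change to sample size and no change to the primary analysis. The downside is that a hazard ratio in confirmed MIBC can no longer be presented as a randomised effect. The possible MIBC stratum also includes patients who turn out to have NMIBC, so it answers the MIBC question less directly.

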14. HEALTH ECONOMIC EVALUATION

An economic evaluation will be performed to estimate the incremental cost-effectiveness of the imaging-directed pathway compared with surgery-directed (standard) pathway for bladder cancer patients from a UK NHS and Personal Social Services (PSS) perspective. Hospital and community health and social care service use, such as inpatient stays, outpatient visits and medication use, will be collected from two principal sources (i) Hospital Episode Statistics (HES) data and (ii) self-reported participant questionnaires. The data collected in the participant questionnaires at each time point will also record direct non-medical costs borne by participants and carers as a result of participant attendance at hospital visits (including travel expenses), as well as indirect costs associated with work losses and impaired health status. Unit costs for each resource input will be obtained from a variety of primary and secondary sources, including national cost compendia such as the Department of Health's National Reference Costs, the British National Formulary and the Personal and Social Services Research Unit (PSSRU) compendium of Unit Costs of Health and Social Care. Participant health-related quality of life will be estimated using the EuroQol measure. Study participants will be asked to complete the EuroQol EQ-5D-5L at baseline and at 3, 6, 9, 12, 18, 24 months and annually from 24 months up to 5 years post-randomisation. Responses to the EQ-5D-5L will be converted into multi-attribute utility scores using newly established algorithms for this measure.

A within study economic evaluation will compare the outcomes and costs for the study comparators over the study follow-up period. First, a cost-consequence analysis will describe all outcomes related to the resource use profiles, costs and health consequences (side-effects, disease progression, recurrences) of the imaging-directed pathway compared with the TURBT directed (standard) pathway for bladder cancer patients. Subsequently, a cost-utility analysis will determine the incremental cost per quality-adjusted life year (QALY) associated with the imaging-directed pathway. Outputs of the economic evaluation will be presented as incremental cost-effectiveness ratios (ICERs); scatterplots of simulated ICER values on cost-effectiveness planes, cost-effectiveness threshold varies across a range of values. Discounting of costs and health consequences will not be required for the within-study economic evaluation. Sensitivity analyses will be used to estimate the between-group differences in mean costs and QALYs. Interaction terms will be used to investigate possible treatment moderators that can identify participant subgroups for whom cost-effectiveness is predictably different, e.g. age, sex, or other relevant participant characteristics.

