7.8 Patient follow-up

Patients will be followed-up every 3 months until 12 months, every 6 months until 24 months and annually from 24 months to 5 years from the date of randomisation.

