12. END OF STUDY DEFINITION

The end of study will be 3 months after the last patient has a minimum of 5 years follow-up. The Study Office will notify the main REC that the study has ended and a summary of the clinical study report will be provided within 12 months of the end of study.

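### The cost-utility analysis is left undiscounted over a follow-up of up to 5 years, so later costs and later QALYs are both overweighted; the documents do not fix which way this moves the ICER

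*Protocol*

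**What the plan says.** Section 14 (Health Economic Evaluation) plans a within-study evaluation that will "compare the outcomes and costs for the study comparators over the study follow-up period". Its main output is a ratio: "a cost-utility analysis will determine the incremental cost per quality-adjusted life year (QALY) associated with the imaging-directed pathway". On discounting it says: "Discounting of costs and health consequences will not be required for the within-study economic evaluation".

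The length of follow-up is set in three places:

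- Section 14 has EQ-5D-5L, the source of the QALYs, completed "at baseline and at 3, 6, 9, 12, 18, 24 months and annually from 24 months up to 5 years post-randomisation".
- Section 7.8 follows patients "annually from 24 months to 5 years from the date of randomisation".
- Section 12 states: "The end of study will be 3 months after the last patient has a minimum of 5 years follow-up".

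The synopsis gives a study duration of 60 months, and Section 13.2.3 sizes the final stage on recurrence at 2 years. Section 14 mentions sensitivity analyses, but none of them concerns discounting.

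**The concern.** If every cost and health effect fell within 12 months of randomisation, an annual discount rate would have nothing to act on and the sentence would be harmless. Here the evaluation runs over several years. The two procedures being compared, MRI and TURBT, come at the start. Recurrence, progression, surveillance, later treatment and survival accrue over years. Without discounting, a cost or a QALY in year 5 carries the same weight as one in year 1.

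This is a stated analysis rule, so it is not a detail left for a later analysis plan. Cost-effectiveness is a listed secondary outcome of the final stage (Table 2), reported as ICERs and across a range of threshold values. A shift of several per cent in the ratio can matter near a threshold.

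**Working it through.** The protocol states no figure on this point, so there is none to reproduce.

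**Inputs.** Horizon: up to 5 years (Sections 7.8, 12 and 14). Rate under the plan: 0%. Discount rate *r*: an assumption, because the protocol gives none; shown at 1.5%, 3.5% and 5% a year.

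**Step 1: weights.** With year 1 undiscounted, year *k* has weight 1/(1+*r*)^(*k*−1). The plan uses 1 throughout. The overstatement of five equal yearly amounts is 5/(sum of weights) − 1. The overweighting of a year-5 amount is (1+*r*)^4 − 1.

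| *r* | Weights, years 1 to 5 | Sum | Constant stream overstated by | Year-5 amount overstated by |
|---|---|---|---|---|
| 1.5% | 1, 0.985, 0.971, 0.956, 0.942 | 4.854 | 3.0% | 6.1% |
| 3.5% | 1, 0.966, 0.934, 0.902, 0.871 | 4.673 | 7.0% | 14.8% |
| 5% | 1, 0.952, 0.907, 0.864, 0.823 | 4.546 | 10.0% | 21.6% |

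Discounting continuously from randomisation, instead of in yearly steps, gives 8.8% in place of 7.0% at 3.5%.

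**Step 2: effect on the ICER.** The ICER is a ratio of increments, so what matters is the timing of incremental cost relative to incremental QALYs. Each hypothetical profile below has an undiscounted ICER of 10,000. Entries are (undiscounted ICER / discounted ICER) − 1.

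| Profile | 1.5% | 3.5% | 5% |
|---|---|---|---|
| All cost in year 1, all QALY gain in year 5 | −5.8% | −12.9% | −17.7% |
| Cost in year 1; gains 0.02, 0.03, 0.05 in years 3, 4, 5 | −4.8% | −10.7% | −14.8% |
| Cost in year 1; gain 0.02 in each year | −2.9% | −6.5% | −9.1% |
| Cost and gain both even over 5 years | 0% | 0% | 0% |
| Gain 0.05 in years 1 and 2; costs 300, 300, 400 in years 3, 4, 5 | +3.9% | +9.3% | +13.5% |

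Worked at 3.5%:

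- First row: the ratio equals the year-5 weight, 0.871, and 0.871 − 1 = −12.9%.
- Third row: 1000/(0.02 × 4.673) = 10,700, and 10,000/10,700 − 1 = −6.5%.
- Last row: discounted cost is 300 × 0.9335 + 300 × 0.9019 + 400 × 0.8714 = 899.2. Discounted gain is 0.05 × (1 + 0.9662) = 0.0983. The discounted ICER is 9,147, and 10,000/9,147 − 1 = +9.3%.

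The −12.9% is the lower limit at 3.5% only if incremental cost and incremental QALYs each keep one sign over time. If an early saving is followed by later extra cost, the net increment can be small and its relative change larger.

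**Step 3: shorter horizon.** Over 2 years at 3.5%, a constant stream is overstated by 2/1.966 − 1 = 1.7% (3.5% in the continuous form). The extreme ICER case, with cost in year 1 and gain in year 2, is 0.966 − 1 = −3.4%.

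**Step 4: can the horizon be one year or less?** Suppose the 60 months in the synopsis include recruitment, and the 12-month feasibility stage and the 30-month final stage (Section 3) run one after the other. The last patient then has 60 − 12 − 30 = 18 months, and the first patients close to 60. Section 12 requires at least 5 years for the last patient. No reading gives a horizon within one year.

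**The case against.** A reader might infer that leaving out discounting flatters pathway 2, on the view that its costs come early and its benefits late. The documents do not support that. Pathway 2 replaces TURBT under general anaesthesia with MRI for possible MIBC, and the protocol's stated hope is to avoid unnecessary surgery and save clinical cost, so pathway 2 may be the cheaper arm at the start. Section 1.1 also describes long-term surveillance of NMIBC, as often as every 3 to 6 months at £533 or more per episode. Those later costs are overweighted in the same way as later QALYs. If pathway 2 were cheaper and better in every year, no discount rate would change the conclusion. This objection stands, and it removes any claim about direction.

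Three further objections stand in part:

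- **Size.** The 13% needs all cost in year 1 and all gain in year 5, and 5 years is the longest horizon. Shorter horizons and similar time profiles give smaller effects or none.
- **Wording.** Saying that discounting is not required is softer than forbidding it, but the protocol plans nothing discounted.
- **Comparability.** One might infer that the result could not be compared with discounted evaluations. That goes too far: the data are collected by time point and can be discounted later.

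The rate itself comes from outside the documents, so every figure here depends on that assumption.

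**Conclusion.** The concern holds in a limited form. The protocol fixes an undiscounted cost-utility analysis over a multi-year horizon and gives no reason for it, so later costs and later QALYs are both overweighted. At an assumed 3.5% a year over 5 years, this is 7.0% for a constant stream and 14.8% for year-5 amounts.

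The ICER may come out too low, unchanged or too high, depending on time profiles that the documents do not give. In the single-sign profiles worked through at 3.5%, the error runs from about 13% too low to about 9% too high, and it is smaller over 2 years. The documents do not support the conclusion that the plan favours either pathway.

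This affects a secondary outcome only. The CPFS comparison, its 380 events and the 950 patients do not depend on it.

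**What to change.** Replace the sentence in Section 14 with:

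> Costs and QALYs arising after the first 12 months will be discounted at a stated annual rate (e.g. 3.5%, an assumption to be confirmed by the sponsor against the reference case it follows), with sensitivity analyses at 0% and 1.5%.

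The 0% analysis keeps the result that the present text would give. The alternative is to state and justify a horizon of one year or less, but that would leave the EQ-5D-5L data from years 2 to 5 outside the evaluation.

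The cost is one sentence and trivial analysis work, with no new data. The reported ICER may move in either direction.
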